2.0 STUDY DESIGN

This is a proof of concept randomized controlled pilot study assessing whether prenylation and membrane localization of Rap1 in PBMCs can be altered in individuals undergoing autologous HCT for MM by administering a daily beta-blocker (propranolol) to 20 participants. Outcomes of patients on this clinical trial will be compared to 20 participants in a control arm. Study assessment time points are detailed in Table 4.7a.

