4.0 ENROLLMENT PROCEDURES

4.1 Patient Enrollment

Patients will be approached for this study during the pre-transplant evaluation phase. Transplant physicians will evaluate the patient eligibility onto the parent study and this ancillary study. Eligible patients willing to participate in the trial will sign an MCW IRB approved informed consent form. A Clinical Trials Office CRC will record the documentation of patient consent and proceed with registration procedures. All source documents that support eligibility including a signed informed consent/HIPAA and signed eligibility checklist, will be available, reviewed and eligibility verified. At the point of registration, a member of the study team will register the patient in the electronic database, including demographics, consent and on-study information. The patient will be assigned a unique sequence number for the study. The principal investigator (PI) of the study, [name], will be notified prior to enrollment. If at any point in time a patient wishes to withdraw from the study, they may notify [name] verbally or in writing. There will be no further data collection for participants who elect to withdraw from the study.

Target enrollment is 40 (20 per group) and includes patients undergoing autologous HCT for MM at MCW. Half of the participants in the parent study will be randomized via permuted block assignment with random block sizes to receive propranolol upon study entry. Informed consent will be obtained to access participants' full medical records to ascertain relevant demographic and medical data as outlined in Section 4.2. The patient must have signed informed consent prior to registration on both studies. Due to the pilot and feasibility nature of this study, the need to monitor response to prophylactic beta-

blocker usage in a medically ill population, as well as the objective nature of Western blot analysis, this pilot study will not be blinded. Patients will be enrolled by Day -7.. Total study duration will be up to 7 weeks for participants assigned to the intervention group (1 week pre-transplant through 6 weeks post-transplant) and 5 weeks for those in the control arm (1 week pre-transplant through 4 weeks post-transplant). Additional clinical information will be collected for 100 days post-transplant as identified in section 3.2.2.2.

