4.5 Rap1 prenylation

Peripheral blood mononuclear cells (PBMCs) will be isolated from the whole blood samples collected from patients at the three designated time points (Baseline, Day -2, and Day +28). Members of [name] laboratory (Professor, Pharmacology and Toxicology, MCW) will conduct western blotting on the cytosolic and membrane fractions of isolated PBMCs to determine the distribution of Rap1 in the different fractions, and the status of Rap1 prenylation in the cells.

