5.2 Sample Size and Power Calculation

We will enroll 40 participants undergoing autologous HCT for MM at MCW. Accounting for study attrition and beta-blocker intolerance, we aim to have 30 patients with a complete set of prenylation data. A targeted final sample of 15 participants in the intervention group will be sufficient for Western blot analysis. This sample size is established for the purpose of the parent study and should be sufficient to describe prenylation.

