5.3 Analysis of Primary Endpoints

5.3.1 Rap1 prenylation by beta-blocker exposure

Western blotting on the cytosolic and membrane fractions of isolated PBMCs will determine the distribution of Rap1 in the different fractions as well as the status of Rap1 prenylation in the cells exposed vs. not exposed to beta-blocker therapy. The statistical difference between cells from patients exposed to beta-blocker therapy (intervention arm) vs. those not exposed to beta-blocker therapy (control arm) will be determined by repeated-measures of analysis of variance (ANOVA) individually at the two blood assessment time points on beta-blocker therapy (Day -2, and Day +30). Baseline Rap1 prenylation will also be assessed by the first blood draw and may be compared to later time points. Patients will be included in final analyses if and only if they have been adherent to the study drug during the designated time period as described in the parent protocol.

References

2. Williams CL. A new signaling paradigm to control the prenylation and trafficking of small GTPases. *Cell Cycle*. 2013;12(18):2933-2934.
4. Linden J. Adenosine promotes tumor metastasis. *Sci Signal*. 2013;6(277):pe20.

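### The only planned Rap1 analysis keeps patients by adherence to study drug, a filter that can act only on the propranolol arm, with no as-randomised analysis beside it

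*Combined protocol and SAP*

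**What the plan says.** Section 2.0 describes a randomised controlled proof-of-concept pilot with 20 patients given propranolol: "Outcomes of patients on this clinical trial will be compared to 20 participants in a control arm". Section 4.1 gives the allocation method ("Half of the participants in the parent study will be randomized via permuted block assignment") and states that the study is not blinded. No placebo is mentioned, and Section 5.3.1 describes the control arm as not exposed to beta-blocker therapy.

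Section 5.3.1 compares the arms by ANOVA at the two on-treatment draws and then restricts the data: "Patients will be included in final analyses if and only if they have been adherent to the study drug during the designated time period". Adherence and its time window are "as described in the parent protocol", which is not among the documents.

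Section 5.2 anticipates losses: "Accounting for study attrition and beta-blocker intolerance, we aim to have 30 patients with a complete set of prenylation data". It adds: "A targeted final sample of 15 participants in the intervention group will be sufficient for Western blot analysis".

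Section 4.1 ends data collection for patients who withdraw from the study. No as-randomised, intention-to-treat or sensitivity analysis of Rap1 appears anywhere.

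**The concern.** Randomisation makes the two arms comparable when they are formed. A rule that later removes patients from one arm, for a reason that cannot arise in the other, gives that protection up. Patients who cannot stay on propranolol around transplant may differ from those who can, for example in how ill they are. Controls with the same characteristics remain in the comparison. If those characteristics also relate to Rap1 prenylation, the arms will differ even when propranolol does nothing.

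The background section says that showing an effect on Rap1 prenylation will support later studies in patients' tumours. A result that mixes drug effect with selection is a weak basis for that step. Without an as-randomised result beside it, the reader cannot judge how much selection contributes.

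**Working it through.** **1. The plan's own figures.** Section 5.2 goes from 40 enrolled to 30 complete: 30/40 = 0.75, a 25% loss. The intervention arm goes from 20 to 15: 15/20 = 0.75. The two agree. The implied number of controls is 30 − 15 = 15. There is no power figure to reproduce, because the plan gives no alpha, power, effect size or SD.

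**2. Which patients the rule can remove.** A control has no study drug to adhere to. The condition in Section 5.3.1 is therefore either undefined for all controls or ignored for them. In the second case, the only workable one, every adherence exclusion comes from the propranolol arm.

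**3. How many.** The target of 15 of 20 allows at most 5 losses in that arm, and Section 5.2 attributes losses to attrition and intolerance together. Five adherence exclusions is therefore the upper case under the target; 1 and 3 are also shown.

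**4. Illustrative bias.** Everything in this step is assumed:
- the drug has no effect;
- Rap1 at Day +28 is y = r·z + √(1 − r²)·e, where z is adherence and z and e are independent standard normal variables;
- the k least adherent of 20 propranolol patients are removed;
- there are 15 or 20 unfiltered controls;
- the test is a two-sided 5% t-test.

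(Section 5.3.1 writes Day +30 for the draw that Section 4.4 and Table 4.7a place at Day +28.)

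The expected shift is r × c, where c is the mean z of those kept: 0.098 (k = 1), 0.259 (k = 3), 0.405 (k = 5). For example, 0.7 × 0.405 = 0.28 SD. Rejection rates come from simulation with 100,000 replicates per cell, and the ranges cover 15 and 20 controls.

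| Removed | r = 0.3 | r = 0.5 | r = 0.7 |
|---|---|---|---|
| 1 of 20 | 0.03 SD; 5.1–5.2% | 0.05 SD; 5.4% | 0.07 SD; 5.8–5.9% |
| 3 of 20 | 0.08 SD; 5.7% | 0.13 SD; 6.8–7.1% | 0.18 SD; 8.8–9.1% |
| 5 of 20 | 0.12 SD; 6.4–6.5% | 0.20 SD; 9.0–9.5% | 0.28 SD; 13.4–14.0% |

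Repeat runs agree to within a few tenths of a percentage point, except at r = 0.7 with 5 removed, where they span about 13% to 14%. At r = 0 there is no shift and rejection is 5.0%. A negative r reverses the sign: at r = −0.7 with 5 removed the shift is −0.28 SD. An as-randomised 20 vs 20 analysis with all outcomes collected holds its error rate at about 5% (4.8% to 5.1% by simulation).

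**5. Scale.** With 15 vs 15, an assumed 80% power and two-sided 5%, the detectable difference is 1.06 SD. The shifts in the table run from 0.03/1.06 = 3% to 0.28/1.06 = 27% of it.

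**The case against.** The restriction fits the stated question. Sections 2.1 and 3.0 ask what beta-blocker administration does to Rap1 in exposed versus unexposed cells, and this is an exploratory pilot with no formal error rate. An as-randomised analysis answers a different question and dilutes any effect. That is fair, and it is why the adherent comparison should stay. It does not justify making it the only analysis of a randomised study.

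The parent protocol is unseen. Its adherence threshold may be loose enough to exclude almost nobody, and it may say how controls are handled. This stands as a limit on the size of the problem. The sentence in Section 5.3.1 would still shut every non-adherent patient out of the Rap1 analysis.

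The upper case is strained. Losing 5 of 20 controls would have to be attrition, since controls cannot be lost to intolerance. If attrition were the same on propranolol, it would use up all 5 planned losses there and leave none for adherence. This is right under the target, so the lower rows of exclusions deserve as much weight as the last. But Section 5.2 names intolerance as a cause of loss, and a target does not cap actual exclusions.

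The correlations are invented, and removing strictly the least adherent is the strongest selection for a given r. The illustration also ignores the Day −2 draw and the optional baseline comparison, which might absorb stable differences between patients. All of this stands. The claim is that the filter may bias the comparison, by an unknown amount in an unknown direction.

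**Conclusion.** The concern holds. As written, the inclusion rule cannot be applied to controls. In its workable reading it selects within one randomised arm on post-randomisation behaviour, and no as-randomised result is planned to set beside it. Those points rest on the text alone.

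The size of any bias rests on assumptions about the number excluded and the link between adherence and Rap1, neither of which the documents give. The illustrated range runs from zero (no correlation), through 0.03 to 0.07 SD with one exclusion, to 0.12 to 0.28 SD with five, in either direction. This should be fixed. It does not invalidate the adherent analysis as an exploratory look at exposure.

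**What to change.** Replace the inclusion sentence in Section 5.3.1 with wording such as:

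> At each time point, all randomised patients with a Rap1 measurement at that time point are analysed in the arm to which they were randomised, regardless of adherence. An analysis of adherent intervention patients versus controls is also reported and labelled non-randomised.

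Two additions are needed:
- State that the scheduled Day −2 and Day +28 draws continue after propranolol is stopped, unless the patient withdraws from the study. Section 4.5 already plans that cells "will be isolated from the whole blood samples collected from patients at the three designated time points", without an adherence condition, so this is a clarification.
- Report by arm and time point the numbers randomised, sampled, adherent and excluded, with reasons. Requiring a sample is itself a post-randomisation condition, although it applies to both arms.

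The direct cost is SAP wording and Western blots on draws already scheduled. The real cost is dilution. Suppose the true effect is 1.06 SD and 1, 3 or 5 of 20 propranolol patients get none of it. The arm difference falls to 1.06 × 19/20 = 1.01, 1.06 × 17/20 = 0.90 or 1.06 × 15/20 = 0.80 SD. As-randomised power at 20 vs 20 is then about 87%, 77% or 65% (about 69% in the last case if the reduced effect is treated as a uniform shift). Adherent-only power against 20 controls is 90%, 88% or 85%, and 80% for 15 vs 15. Reporting both analyses keeps the more sensitive one and lets the reader see whether selection matters.

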5.1.2 Primary Endpoint

The primary endpoint is Day +28 (4 weeks) following HCT for MM, with intervention arm patients followed for an additional 1-2 weeks until they are weaned from beta-blocker therapy.

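### One adherence rule governs two separately tested draws; if its period runs past Day -2, patients who stop later lose a valid Day -2 result

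*Combined protocol and SAP*

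**What the plan says.** Section 5.3.1 of the combined protocol and SAP tests the difference between arms "individually at the two blood assessment time points on beta-blocker therapy", naming Day -2 and Day +30. Sections 4.4 and 4.5 and Table 4.7a put the later draw at Day +28.

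The same section ends with the inclusion rule: "Patients will be included in final analyses if and only if they have been adherent to the study drug during the designated time period". The sentence continues by reference: adherence is judged "during the designated time period as described in the parent protocol". No separate rule is given for Day -2, and neither the length of the period nor the adherence threshold appears in this document.

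On exposure, section 5.1.2 sets the primary time point at Day +28, "with intervention arm patients followed for an additional 1-2 weeks until they are weaned from beta-blocker therapy". Section 4.1 agrees: "Total study duration will be up to 7 weeks for participants assigned to the intervention group", ending six weeks after transplant. Section 5.2 enrols 40 and aims for 30 patients with complete data, 15 of them in the intervention arm, after allowing for attrition and drug intolerance.

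**The concern.** Stopping propranolol after the Day -2 draw cannot change the Rap1 measured at that draw. A patient who took the drug as intended up to Day -2 gives a valid on-drug observation there, whatever follows. A single rule for all final analyses, over a period that continues past Day -2, would remove that observation because of something that had not yet happened.

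Two things are at stake. The first is the loss of usable samples in a pilot of 20 per arm. The second is selection: the intervention arm at Day -2 would consist of patients who went on to tolerate the drug through conditioning and transplant. Table 4.7a requires the Day -2 draw to precede any conditioning, so it is the only on-drug sample free of conditioning and transplant effects. It would be a pity to let tolerance during those events decide who is in it. Section 1.2 suggests that the first 30 days after transplant may be the time of highest beta-adrenergic signalling, so later tolerance could plausibly be related to the pathway under study.

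An as-randomised comparison alone would not repair the adherent-only analysis at Day -2, which needs a rule matched to the draw.

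**Working it through.** **Which reading the text favours**

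- The comparisons are plural and made one draw at a time; the adherence period is singular and applies to the patient, not to the draw.
- Therapy continues past Day +28 (sections 4.1 and 5.1.2), so the period of intended drug use extends well beyond Day -2.
- Section 5.2 counts patients with complete data, which fits exclusion of whole patients.
- Against this, the period is set in the parent protocol, which is not among the documents. It could be defined per draw.

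**The plan's own numbers**

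Loss implied overall: 1 - 30/40 = 25%. In the intervention arm: 1 - 15/20 = 25%. Inflating back, 30/0.75 = 40 and 15/0.75 = 20. The figures agree with each other, but the 25% is back-calculated, so this shows only internal consistency. The implied number of complete controls is 30 - 15 = 15, also a loss of 5 of 20. There is no power statement to reproduce: section 5.2 gives no alpha, effect size or SD.

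**How many patients could be affected**

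Planned intervention losses are 20 - 15 = 5. These combine attrition and intolerance, with no split and no timing. The number who were adherent at Day -2 and stopped later is therefore between 0 and 5.

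**Effect on Day -2 power (illustration)**

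Assumed, not from the documents: two-sided 5%, true difference 0.9 SD, two-sample t-test, all 20 controls available. The noncentrality is 0.9 / sqrt(1/n1 + 1/20), on n1 + 18 degrees of freedom.

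| Intervention patients at Day -2 | Noncentrality | Power |
|---|---|---|
| 15 | 2.63 | 72.5% |
| 17 | 2.73 | 75.6% |
| 19 | 2.81 | 78.1% |

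Recovering two patients gains about 3 points; recovering four gains 5.6. With an assumed difference of 0.5 SD, going from 15 to 19 moves power only from 29.5% to 33.0%.

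**Effect on the Day -2 mean (illustration)**

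If k late stoppers among 20 differ from the rest by d SD at Day -2, removing them shifts the intervention mean by (k/20) x d.

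| d (assumed) | k = 1 | k = 5 |
|---|---|---|
| 0.5 SD | 0.025 SD | 0.125 SD |
| 1.0 SD | 0.05 SD | 0.25 SD |

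The documents give neither k nor d, and the direction of the shift is unknown.

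**The case against.** The strongest objection is that the period is defined elsewhere. The parent protocol may set it per draw, in which case no late stopper is lost at Day -2. A reader might infer that the plan certainly removes such patients. The documents do not establish that, and the study durations in sections 4.1 and 5.1.2 describe follow-up rather than the adherence period. This stands, and the point is conditional for that reason.

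A reader might also reason that Day -7 to Day -2 covers 5 of the 35 days to Day +28, so with stopping equally likely each day, 5 x (1 - 5/35) = 4.3 of the 5 planned losses would be valid Day -2 samples. The documents do not support that either. Uniform stopping has no source, and early intolerance would lower the figure. Section 5.2 also names attrition as a cause, and the same 5 are implied lost among controls, who have no study drug to tolerate. Attrition alone could account for all 5.

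The power and bias figures rest on assumed inputs and a two-sample t-test, whereas the plan names repeated-measures ANOVA. No section links later tolerance to Rap1 at Day -2. These limits stand.

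It can be said, too, that an as-randomised comparison would already retain every available Day -2 sample, and that one common patient set at both draws is a defensible choice. The first is true but leaves the adherent-only analysis as it is. The second gives a uniform n at the price of conditioning an earlier outcome on a later event.

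**Conclusion.** The point holds conditionally. As written, one patient-level rule covers two separate comparisons, nothing ties Day -2 inclusion to adherence up to Day -2, and the period is not stated here. If it runs past Day -2, which is the natural reading, late stoppers are dropped from a comparison that their stopping could not have affected.

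The size is uncertain and probably modest: 0 to 5 of 20 intervention patients within the planned loss, and a power gain of about 3 to 6 points at Day -2 if two to four are recovered under the assumptions above. Avoiding selection on a later event is a better reason for the change than the power gain.

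It would be too strong to infer that the primary time point is compromised. Adherence up to Day +28 is the relevant window there, so a per-draw rule changes little at that draw; it matters only for someone who stops after Day +28, if the period extends into weaning. This should be corrected before analysis, but it does not call the trial's main comparison into question.

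**What to change.** Replace the closing rule of section 5.3.1 with wording such as: *For the adherent-only analysis, adherence is judged separately for each draw, from first dose up to that draw. A patient adherent up to Day -2 is included at Day -2 whatever happens later.* State the period and the adherence threshold in this plan instead of only by reference, report n by arm at each draw, and present an as-randomised comparison of all available samples alongside. The Day +28 and Day +30 labels for the later draw should be reconciled at the same time, since the window depends on them.

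The cost is wording, with no new visits or samples; adherence has to be datable relative to each draw. The small downside is that the adherent sets at the two draws may differ, so a change between draws in that analysis partly reflects a change in who is included. If the parent protocol already sets the period per draw, the new text only makes that visible here.
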